11.1.1 Other significant adverse events

During the evaluation of the AE data, an AstraZeneca medically qualified expert will review the list of AEs that were not reported as SAEs and Discontinuation of Investigational Product due to Adverse Event (DAE)s. Based on the expert's judgement, significant AEs of particular clinical importance may, after consultation with the Global Patient Safety Physician, be considered other significant adverse events (OAEs) and reported as such in the CSR. A similar review of laboratory/vital signs/ECG data will be performed for identification of OAEs.

Examples of these are marked hematological and other laboratory abnormalities, and certain events that lead to intervention (other than those already classified as serious), dose reduction or significant additional treatment.

11.2 Calculation or derivation of pharmacokinetic variables

The PK analyses of the TC-5214 plasma, urine, and dialysate concentration data will be performed at [REDACTED]. Pharmacokinetic analyses will be conducted according to [REDACTED] SOPs for PK analyses. The actual sampling times will be used in the PK parameter calculations. Pharmacokinetic parameters will be derived using noncompartmental methods with WinNonlin[®] Professional Version 5.2, or higher, (Pharsight Corp., Mountain View, California). All PK computations will be performed using WinNonlin Professional[®] 5.2, or higher; or SAS[®] Version 9.1, or higher (SAS Institute, Inc., Cary, North Carolina). Graphics may be prepared with SAS Version 9.1, or higher; SigmaPlot[®] 9.0, or higher (Systat Software, Inc., San Jose, California); or WinNonlin Professional[®] 5.2, or higher. Nominal times will be used for any interim PK analyses, if applicable.

Where possible, the following plasma PK parameters will be determined for TC-5214:

- Maximum plasma concentration (C_{max} , ng/mL), obtained directly from the observed concentration versus time data

- Time to maximum plasma concentration (t_{\max} , h), obtained directly from the observed concentration versus time data
- Terminal rate constant (λ_z). Visual assessment will be used to identify the terminal linear phase of the concentration-time profile. A minimum of 3 data points, with an Rsq of greater than or equal to 0.8 will be used for determination.
- Terminal half-life ($t_{1/2\lambda_z}$, h)
- Area under the plasma concentration-time curve from zero to the time of the last measurable concentration [$AUC_{(0-t)}$]
- Area under the plasma concentration-time curve from 4 to 8 hours [$AUC_{(4-8)}$] to match the dialysis period, Group 5, Treatment Period 2, Part 1, only
- Area under the plasma concentration-time curve from 72 to 76 hours [$AUC_{(72-76)}$] to match the dialysis period, Group 5, Part 2, only
- Area under the plasma concentration-time curve from zero to infinity (AUC) calculated by linear up/log down trapezoidal summation and extrapolated to infinity by addition of the last quantifiable concentration divided by the elimination rate constant: $AUC_{(0-t)} + C_{\text{last}}/\lambda_z$. If the extrapolated area ($C_{\text{last}}/\lambda_z$) is greater than 30% of AUC, then AUC will not be reported
- Apparent plasma clearance (CL/F, L/h)
- Apparent volume of distribution (V_z/F , L)

The following plasma PK parameters will be calculated for diagnostic purposes and listed, but will not be summarized:

- The time interval (h) of the log-linear regression used to determine $t_{1/2\lambda_z}$
- Number of data points included in the log-linear regression analysis
- Goodness of fit statistic for calculation of λ_z (Regression coefficient)
- Percentage of AUC obtained by extrapolation (%AUC_{ex}).

Where possible, the following urine PK parameters will be determined for TC-5214:

- Cumulative amount of drug excreted unchanged into urine from zero to time t hours ($A_{e(0-t)}$, mg). The amount will be calculated and reported for each collection interval and cumulatively

- Fraction of dose excreted as unchanged drug into urine (f_e ; % dose). The fraction will be calculated and reported for each collection interval and cumulatively
- Renal clearance (CL_R , L/h), calculated as $A_{e(0-t)}$ divided by $AUC_{(0-t)}$

For Group 5, Part 1, Treatment Period 2, the following PK parameters for TC-5214 will be derived using the dialysate concentrations:

- Cumulative amount of drug extracted unchanged into the dialysate over the dialysis period (time: 4 hours postdose to 8 hours postdose) ($Ad_{(4-8)}$, mg). The amount will be calculated and reported for each 1-hour dialysate collection interval, and cumulatively
- Fraction of dose extracted unchanged into the dialysate over the dialysis period ($fd_{(4-8)}$; % dose). The fraction will be calculated and reported for each collection interval and cumulatively.
- Dialysate clearance (CL_D , L/h), calculated as $Ad_{(4-8)}$ divided by $AUC_{(4-8)}$

For Group 5, Part 2, the following PK parameters for TC-5214 will be derived using the dialysate concentrations:

- Cumulative amount of drug extracted unchanged into the dialysate over the dialysis period (time: 72 hours postdose to 76 hours postdose) ($Ad_{(72-76)}$, mg). The amount will be calculated and reported for each 1-hour dialysate collection interval, and cumulatively
- Fraction of dose extracted unchanged into the dialysate over the dialysis period ($fd_{(72-76)}$; % dose). The fraction will be calculated and reported for each collection interval and cumulatively.
- Dialysate clearance (CL_D , L/h), calculated as $Ad_{(72-76)}$ divided by $AUC_{(72-76)}$

Additional PK parameters may be calculated if deemed appropriate.

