Regression models will be used to assess and quantify the relationship between renal function, as measured by the eGFR, and TC-5214 dose-normalized primary pharmacokinetic parameters (C_{max} and AUC). The initial model will specify a linear relationship between primary pharmacokinetic parameters and the eGFR, and will be estimated using ordinary least squares. Log-transformations may be used to improve model fit. Models which are non-linear in the model parameters will be used in the event that linear models do not yield an adequate fit. Model parameters, 90% CI and p-values will be reported. From the final models, estimates of the mean pharmacokinetic parameters and 90% CI will be made at the median eGFR of each of the renal function groups, as will the differences (or ratios) and 90% CI relative to the control subjects with normal renal function.

As an exploratory analysis, the renal function groups will be compared using a one-way analysis of variance model on the log-transformed dose-normalized primary pharmacokinetic parameters (C_{max} and AUC). The renal impairment groups will be compared to the control subjects with normal renal function (Group 1), with the latter as reference. Geometric least-squares means with corresponding 95% CI and ratios of geometric least squares with corresponding 90% CI will be presented. While this study is not statistically powered in terms of claiming no effect of renal impairment on TC-5214 exposure, interpretation of the effect of renal impairment will be based on point estimates and associated 90% confidence intervals.

Comparisons of pharmacokinetic parameters for subjects in Group 5 with endstage renal disease on a nondialysis day with those on a dialysis day will be performed using a paired t-test (C_{max} and AUC).

	PAGE
TITLE PAGE	1
PROTOCOL SYNOPSIS.....	2
TABLE OF CONTENTS.....	7
LIST OF ABBREVIATIONS AND DEFINITION OF TERMS	12
1. INTRODUCTION	15
1.1 Background	15
1.2 Research hypothesis.....	15
1.3 Rationale for conducting this study	15
1.4 Benefit/risk and ethical assessment	16
2. STUDY OBJECTIVES.....	16
2.1 Primary objective.....	16
2.2 Secondary objectives	16
2.3 Exploratory objectives	16
3. STUDY PLAN AND PROCEDURES	17
3.1 Overall study design and flow chart	17
3.1.1 Part 1	17
3.1.1.1 Part 1, Groups 1 through 3	17
3.1.1.2 Part 1, Group 5	17
3.1.2 Part 2	18
3.1.2.1 Part 2, Groups 1 through 3	18
3.1.2.2 Part 2, Group 5.....	18
3.2 Rationale for study design, doses and control groups.....	28

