Subjects in Groups 1 through 3 will not be on dialysis. They will be admitted to the clinic the morning of Day -1, or on Day -2 at the discretion of the Investigator. Time-matched vital signs will be collected on Day -1. Subjects will then receive a single oral dose of TC-5214 on Day 1 and will remain in the clinic until the completion of the study assessments and procedures scheduled on Day 6. Subjects will return to the clinic for a follow-up visit 7 to 10 days following discharge from the clinic. Subjects in Group 1 who withdraw from the study prior to completion of all PK sample collections may be replaced; subjects in Groups 2 and 3 who withdraw from the study prior to completion of all PK sample collections may be replaced to ensure a minimum of 6 subjects complete the treatment period.

During Part 2, subjects in Groups 1 through 3 will have blood and urine samples collected through 120 hours postdose.

3.1.2.2 Part 2, Group 5

The remainder of subjects enrolled into Group 5 will participate in 1 treatment period, and receive a single oral dose of TC-5214. They will be admitted to the clinic the morning of Day -1, or on Day -2 at the discretion of the Investigator. Time-matched vital signs will be collected on Day -1. Subjects will then receive a single oral dose of TC-5214 on Day 1 after

completion of their first inpatient dialysis session, and will remain in the clinic until the completion of the study assessments and procedures scheduled on Day 6.

[figure not shown]
Pharmacokinetic blood samples will be collected after a single oral dose (Day 1) for up to 120 hours postdose. Samples will be collected through 72 hours postdose (assessment between dialysis) and between 72 and 120 hours (assessment during dialysis).

Pharmacokinetic urine samples will be collected for up to 120 hours postdose from subjects who are able to produce urine.

Subjects will return to the clinic for a follow-up visit 7 to 10 days following discharge from the clinic. Subjects who withdraw from the study prior to completion of all pharmacokinetic sample collections may be replaced at the discretion of the Sponsor.

For details on Part 2 see the Study Flow Charts ([Figure 1](#) and [Figure 3](#)) and the Study Plan [Table 2](#) below.

Figure 1: Study Flow Chart Groups 1 through 3

[figure not shown]
^a Visit 1 may be conducted over 1 or more days during the screening period.

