3.2 Rationale for study design, doses and control groups

The purpose of this study is to determine if renal impairment will affect the PK of TC-5214. The study is designed using the principals embodied in the Food and Drug administration guidance on drug renal impairment studies ([Cockcroft 1976](#)).

For control subjects with normal renal function and subjects with mild renal impairment, a 8 mg dose of TC-5214 was chosen because it is the highest daily dose that will be administered in Phase III trials and was shown to be well tolerated in healthy subjects in previous studies. For subjects with moderate and severe renal impairment, to minimize the effects of compensatory changes such as significant hypotension, a 2 mg dose will be administered.

In order to avoid bias due to demographic differences between the control subjects with normal renal function and subjects with renal impairment, the control group will be matched to the mean demographic characteristics of the **3** renal impairment groups with an allowable variability in age of +/- 10 years and in BMI of $\pm 3 \text{ kg/m}^2$. Sex will be matched to achieve similar distribution between male and female subjects. Only control subjects with stable chronic medical conditions will be included.

Based on available data to date, the mean terminal half-life ($t_{1/2,\lambda_z}$) of TC-5214 in human plasma is approximately 8 to 9 hours. Based on limited interim PK data in 2 subjects with moderate impairment, and 2 subjects with ESRD, renal impairment has been shown to increase the half-life of TC-5214 by approximately 3 and 10 fold, respectively.

For Groups 1 to 3, the study design has been updated to extend the sampling period to 120 hours postdose to adequately characterize the elimination phase of TC-5214 and more accurately determine TC-5214 PK parameters (eg $t_{1/2,\lambda_z}$, AUC, and CL/F). For Group 5 it was determined that a single dose of TC-5214 administered after the completion of a dialysis session, with the collection of blood samples for PK through 120 hours postdose (including a 4 hour dialysis session beginning approximately 72 hours postdose) would enhance patient safety.

The PK profile in patients with severe renal failure will be extrapolated from the data in subjects on dialysis obtained between their dialysis sessions, thus subjects with severe renal impairment (eGFR <30 mL/min) will not be recruited for this study.

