6.4.1.1 Blood Samples

Blood samples (approximately 6 mL, split into 2 tubes, collected in K2 EDTA tubes) for determination of TC-5214 in plasma will be taken on the days presented in the study plans [Table 1](#) and [Table 2](#).

Part 1:

For Group 1, Group 2, and Group 3 blood PK samples will be collected at predose, 1, 1.5, 2, 2.5, 3, 4, 6, 8, 12, 24, 36, 48, and 72 hours postdose.

For Group 5, Part 1, blood PK samples will be collected at predose, 1, 1.5, 2, 2.5, 3, 4, 6, 8, 12, 24, 36, 48, and 72 hours postdose. For Treatment Period 2, the timing of sample collections is the same as for Treatment Period 1, however, the sample scheduled for collection at 4 hours must be collected immediately before dialysis start, and the sample scheduled at 8 hours must be collected immediately after dialysis completion rather than strictly adhering to the scheduled sampling times at 4 and 8 hours. For Treatment Period 2, the blood samples during and surrounding the hemodialysis session will be collected from predialyzer lines.

Part 2:

For Part 2, Group 1, Group 2, and Group 3, blood PK samples will be collected at predose, 1, 1.5, 2, 2.5, 3, 4, 6, 8, 12, 24, 36, 48, 72, 96, and 120 hours postdose.

For Group 5, Part 2, blood PK samples will be collected at predose, 1, 1.5, 2, 2.5, 3, 4, 6, 8, 12, 24, 36, 48, 72, 74, 76, 96, and 120 hours postdose. The sample scheduled for collection at 72 hours must be collected immediately before dialysis start, and the sample scheduled at 76 hours must be collected immediately after dialysis completion rather than strictly adhering to the scheduled sampling times. Blood samples during and surrounding the hemodialysis session will be collected from predialyzer lines.

The date and time of collection of each sample will be recorded on the pCRF. For blood volume, see Section 7.1.

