data and dose-normalized PK parameters will be presented by renal function. Figures of PK parameters will also be presented by dose. Individual subject concentration-time data will be graphically presented on linear and semi-logarithmic scales.

For Groups 1 through 3 and Group 5, (Part 1, Treatment Period 1 and Part 2), regression models will be used to assess and quantify the relationship between renal function, as measured by eGFR, and TC-5214 dose-normalized primary pharmacokinetic parameters (C_{max} and AUC). The initial model will specify a linear relationship between primary pharmacokinetic parameters and eGFR and will be estimated using ordinary least squares. Log-transformations may be used to improve model fit. Non-linear models will be used if there is statistical evidence of departure from linearity at the 0.10 significance level. Further, models which are non-linear in the model parameters may be used if simpler models do not provide adequate fit. Model parameters, 90% CI and p-values will be reported. From the linear and final models, estimates of the mean pharmacokinetic parameters and 90% CI will be made at the median eGFR of each of the renal function groups, as will the differences (or ratios) and 90% CI relative to the normal renal group (at the group median eGFR).

As an exploratory analysis, the renal function groups will be compared using a one-way analysis of variance model on the log-transformed dose-normalized primary pharmacokinetic parameters (C_{max} and AUC). The renal impairment groups will be compared to the control subjects with normal renal function (Group 1), with the latter as reference. Geometric least-squares means with corresponding 95% CI and ratios of geometric least squares with corresponding 90% CI will be presented.

Comparisons of PK parameters for subjects in Group 5, Part 1, with ESRD between the two treatment periods (ie on a non dialysis day with those on a dialysis day) will be performed using a paired t-test (C_{max} and AUC).

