2. Given the prolonged elimination half-life of TC-5214 in and high percentage of the AUC requiring extrapolation in subjects with renal impairment, the blood and urine sampling collection intervals for TC-5214 PK sampling time will be extended to 120 hours postdose for Groups 1, 2, and 3 to allow for a more reliable estimation of TC-5214 elimination.
3. Urine will be collected for ESRD subjects in Group 5 who are able to produce urine output, which will allow us to obtain a more complete PK profile in these subjects as both total and renal clearance will then be able to be calculated.
4. Due to the greatly reduced TC-5214 plasma clearance in patients on dialysis, it will be possible to estimate TC-5214 PK from data obtained between and during dialysis after a single dose, so a second study period is not required, thus ESRD subjects in Group 5 will participate in only 1 treatment period, and receive only a single dose of TC-5214.

The protocol for the study is to be amended as follows:

Section of protocol affected:

Page 2, Protocol Synopsis, Study center(s) and number of subjects planned

Previous text:

Eight subjects in each category of mild, moderate, severe renal impairment, end stage renal disease requiring dialysis, and 8 male or female subjects without renal impairment will be dosed for a total of approximately 40 evaluable subjects to complete the study.

Revised text:

Eight subjects in each category of mild, moderate renal impairment, end stage renal disease requiring dialysis, and 8 male or female subjects without renal impairment will be dosed for a total of approximately **32** evaluable subjects to complete the study.

Reason for Amendment:

Subjects with severe renal impairment (Group 4) will not be recruited for this study, reducing the number of evaluable subjects to approximately 32.

Section of protocol affected:

Page 3, Protocol Synopsis, Study design

Previous text:

Subjects will be enrolled into 1 of 5 groups in parallel, according to their degree of renal impairment based on their estimated glomerular filtration rate (eGFR), determined using the abbreviated, 4-variable Modification of Diet in Renal Disease formula as follows:

Group 1: control subjects with normal renal function: eGFR greater than 80 mL/min

Group 2: mild renal impairment: eGFR greater than or equal to 50 to 80 mL/min

Group 3: moderate renal impairment: eGFR greater than or equal to 30 to less than 50 mL/min

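### Section 11.2 runs the Group 5 Part 2 AUC across the 72–76 h dialysis, and Section 12.2.3 pools it with off-dialysis AUCs in the eGFR regression

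*Supplement*

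**What the plan says.** All references are to the revised protocol, including Amendment 1. No separate SAP is among the documents.

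- **Sampling.** In Part 2, Group 5 is dosed after a dialysis session. Section 6.4.1.1 sets the late samples at "48, 72, 74, 76, 96, and 120 hours postdose. The sample scheduled for collection at 72 hours must be collected immediately before dialysis start", with the 76 h sample immediately after dialysis ends.
- **AUC.** Section 11.2 defines AUC(0-t) as "Area under the plasma concentration-time curve from zero to the time of the last measurable concentration". Total AUC is that area "extrapolated to infinity by addition of the last quantifiable concentration divided by the elimination rate constant". It is not reported if more than 30% is extrapolated. λz needs at least 3 visually chosen points and Rsq of 0.8 or more. The only plasma area added for Part 2 is AUC(72-76), the dialysis window itself.
- **Analysis.** Section 12.2.3: "For Groups 1 through 3 and Group 5, (Part 1, Treatment Period 1 and Part 2), regression models will be used". Part 1 Treatment Period 2, the period with dialysis 4 h after dosing, is left out.
- **Intended use.** Section 3.1.2.2 labels the samples to 72 h as the between-dialysis assessment and the later ones as the during-dialysis assessment. Section 3.2 says the profile in severe renal failure "will be extrapolated from the data in subjects on dialysis obtained between their dialysis sessions". Item 4 of the Amendment 1 rationale says "it will be possible to estimate TC-5214 PK from data obtained between and during dialysis after a single dose", without giving a method.
- **Interpretation.** AUC is a primary parameter, and the synopsis says "interpretation of the effect of renal impairment will be based on point estimates and associated 90% confidence intervals".

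**The concern.** The plan separates exposure between dialyses from exposure during dialysis, and it keeps the dialysis period of Part 1 out of the regression. The AUC formula does not carry that separation into Part 2. If the 120 h sample is quantifiable, both the measured area and the extrapolated tail include the loss caused by dialysis. The regression then mixes two quantities under one name: Period 1 AUC with no dialysis, and Part 2 AUC with one dialysis. CL/F, calculated from the same AUC, is raised correspondingly.

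The direction matters. TC-5214 is cleared mainly by the kidney (Section 1.3), and orthostatic hypotension is the main safety concern (Section 1.4). No severe, undialysed subjects are now studied. An ESRD AUC lowered by dialysis would understate the exposure of a patient who is not dialysed.

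The 30% rule compounds the problem. At the interim half-life, Period 1 AUCs (sampled to 72 h) would probably be withheld, and Section 12.2.1 lets missing values simply reduce n. Amendment 1 planned 4 more ESRD subjects. The ESRD end of the AUC regression could be nearly empty, or could rest on dialysis-lowered values.

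**Working it through.** The plan gives no figure of its own to reproduce.

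**Inputs from the protocol.** Half-life is 8–9 h with normal function and about 10-fold longer in ESRD (Section 3.2, 2 ESRD subjects), so 80–90 h. Dialysis lasts 4 h from about 72 h. The last sample is at 120 h.

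**Assumptions.** One compartment, ka = 1/h, and a plasma fall E of 10–50% over the session beyond natural elimination. E is not in the documents.

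**1. Direction.** Under linear PK, the amount cleared by the body itself is CL × AUC, so AUC = (F·Dose − Ad)/CL. Without dialysis it is F·Dose/CL. The ratio is 1 − Ad/(F·Dose) = 1 − fd(72-76)/F. This holds even with a correct λz.

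**2. Share of AUC beyond time T without dialysis.** With k = ln 2 / half-life, the share is about e^(−kT)/(1 − k) when ka = 1/h. At 85 h, k = 0.00815:

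- T = 72 h: 0.556/0.992 = 56%
- T = 120 h: 0.376/0.992 = 38%

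| Half-life | Beyond 72 h | Beyond 120 h |
|---|---|---|
| 60 h | 44% | 25% |
| 80 h | 54.1% | 35.7% |
| 85 h | 56.1% | 37.9% |
| 90 h | 57.9% | 40.0% |

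At 80–90 h, stopping at 72 h or running to 120 h both exceed 30% when dialysis has no effect.

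**3. Size of the lowering at 85 h, true λz.** A hand approximation is ratio ≈ 1 − 0.561 × E. The full linear-up/log-down calculation at the Part 2 sampling times gives:

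| E | AUC / off-dialysis AUC | Extrapolated | 30% rule |
|---|---|---|---|
| 10% | 0.944 | 36.1% | withheld |
| 20% | 0.889 | 34.1% | withheld |
| 30% | 0.834 | 31.8% | withheld |
| 40% | 0.779 | 29.2% | reported |
| 50% | 0.723 | 26.2% | reported |

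So the AUC is about 6–28% low. If E is instead the total fall, natural elimination included, the range is 4–27%.

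**4. When a value is reported.** The AUC meets the 30% rule only once E reaches about 29% (80 h), 37% (85 h) or 44% (90 h). By then it is about 15%, 20% or 25% low. Over 3 half-lives × 5 falls, 6 of 15 cases are reported, 16–29% low, and 9 are withheld. The 80 h, 30% case is borderline. At 60 h all five are reported, 4–22% low.

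**5. If λz is fitted across dialysis (48–120 h).** At 80–90 h the AUC ratio is 0.71–0.74 for E = 30% (Rsq about 0.89–0.90) and 0.60–0.64 for E = 50% (Rsq about 0.80–0.81). The Rsq rule would not reliably stop such a fit.

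**6. Correction.** Multiplying by Dose/(Dose − Ad(72-76)) restores the ratio to 0.999 in all five 85 h cases (F = 1). A two-compartment check with rebound gave fd of 0.062, 0.111 and 0.182 with AUC ratios of 0.938, 0.889 and 0.818, so the identity in step 1 also holds there.

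**The case against.** The strongest reply is that this is a detail for a PK analysis plan. Section 11.2 refers to SOPs, allows visual choice of the terminal phase and permits additional PK parameters. The study is exploratory, its intervals are descriptive, and Ad, fd, CL_D and the extrapolated percentage are derived anyway, so a reader could see how much drug was dialysed. This lowers the stakes but does not remove the point. The written formula already yields a value, and Section 12.2.3 already sends it to the regression. Neither careful λz selection nor an optional unnamed parameter changes that.

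Four stronger readings are tempting and not supported:

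- A reader might infer that ESRD exposure will be reported low by a known amount. The documents give no dialysis removal, and the half-life rests on 2 subjects. In most of the 80–90 h cases the AUC is withheld, and that comes largely from the 30% rule: with no dialysis effect it is withheld as well.
- A reader might infer that the severe-impairment extrapolation rests on the regression AUC. Section 3.2 does not say which quantity it will use.
- A reader might infer that the overall conclusion would reverse. With an assumed true 10-fold AUC ratio, the result would read 9.4 to 7.2, still a very large effect, and no dosing threshold is stated.
- A reader might infer that Part 1 Period 1 has the same fault because it lists a 72 h sample. Section 3.1.1.2 ends that period at the next dialysis.

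The reply that pre-dialysis λz is fragile also stands. In simulated 24–72 h profiles (4 points, 85 h half-life), about 3%, 38% and 61% miss Rsq 0.8 at assumed residual errors of 5%, 10% and 15%. The fix must allow for this.

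**Conclusion.** The point holds. As written, the Group 5 Part 2 AUC and CL/F include one dialysis session, and that AUC is pooled with off-dialysis Period 1 values in the main regression of a primary parameter. The direction is certain under linear PK for any removal above zero. The size is conditional: about fd(72-76)/F, or 6–28% low for an assumed 10–50% fall at 85 h and 4–22% at 60 h. If removal is small, the lowering is small, but at 80–90 h the AUC is then withheld. Either outcome leaves the ESRD end of the regression poorly served. Cmax should not be affected, since the peak comes well before 72 h. The change should be made, but it is not a fatal fault.

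**What to change.** In Sections 11.2 and 12.2.3, state for Group 5 Part 2:

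1. The AUC used in the regression and ANOVA is an off-dialysis AUC: the AUC using samples through 120 h, extrapolated to infinity, multiplied by Dose/(Dose − Ad(72-76)), with Dose and Ad in the same free-base units.
2. λz comes from points that do not straddle the dialysis session.
3. The uncorrected AUC is listed and labelled as including one dialysis.

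For Group 5 generally, report with a flag, rather than withhold, any AUC that exceeds 30% extrapolation or whose λz misses Rsq 0.8. Run the regression with and without the flagged values. Scaling leaves the extrapolated share unchanged (26–36% in the 85 h cases), so without this rule many corrected values would still be lost.

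The cost is a few sentences. Section 6.4.1.4 already collects the entire dialysate and Section 11.2 already derives Ad(72-76). There are three downsides. The correction takes F near 1; for the same dialysate amounts, F of 0.9 would call for a corrected AUC 0.7–4.4% higher. Incomplete dialysate recovery would under-correct. λz is imprecise because it spans only about half a half-life at 85 h: 48/85 = 0.56 for 24–72 h, or 44/85 = 0.52 for 76–120 h.
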